## **7.9. Concomitant Medications and Non-Drug Therapies**

### **7.9.1. Permitted Medications and Non-Drug Therapies**

All concomitant medications and those taken within 6 months prior to Screening, including over-the-counter and herbal remedies, will be recorded in the eCRF. Non-medication therapies related to the subject's DLB (e.g. neurostimulation, cognitive rehabilitation) that have occurred in the 12 months prior to Screening must also be recorded. The name of the drug, the dose, indication and route of administration as well as the dates administered should be documented; the minimum requirement is to record the drug name and dates of administration. Any medication not specified in the list of prohibited and conditional medications provided in [Table 1](#) is permitted during the study.

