### 8.1. Time and Events

The Time and Events Schedule ([Table 2](#)) displays each study assessment and procedure along with the time of occurrence. All study assessments should be conducted by the investigator, and/or a suitably qualified designee approved and documented for this study. With the exception of the determination required in inclusion criterion #1, all study assessments and determinations may be delegated by the investigator to a suitably qualified designee approved and documented for this study. A qualified physician should be responsible for all study-related medical decisions and care. If the principal investigator is not a physician, he/she must delegate medical decisions and care to a qualified physician. All raters will be trained and certified to perform the specific rating scales in this study.

For Visit 3 there is a visit window of +5 days. For Visits 4 through 12, there is a visit window of  $\pm 5$  days (in relation to the Baseline visit). It is important that all visits should be scheduled relative to the Baseline visit, except for Visit 13. If the visit window is used, the subsequent visit should remain according to the planned visit schedule (i.e., the subsequent visit date should not be re-calculated from the date of the previous visit but should remain relative to Baseline).

Information will be recorded in the source documents and, where appropriate, the eCRF.

If, during the visit, the subject is unable or, in the judgment of the investigator, unlikely to be able to complete the cognitive assessments, the testing may be rescheduled within the windows described previously.

Subjects may be given breaks during the assessments or may have assessments split across different days so long as all assessments are completed within the visit window. Individual assessments or cognitive batteries such as the CDR computerized assessment system should, however, be completed within a single day.

Every effort should be made to administer the CDR computerized assessment system within  $\pm 1$  hour of the time of day of the Baseline administration on subsequent visits for each subject due to the potential for circadian fluctuation in scores. This should be taken into consideration when scheduling and performing Baseline CDR System assessments.

The order of rating scales should, when possible, be held constant, with the CDR computerized assessment system given to the subject first at each visit.

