### **8.3.1.2. Unified Parkinson's Disease Rating Scale – Part III (UPDRS-III)**

The UPDRS-III is a widely used scale designed to follow the longitudinal course of Parkinson's disease. It is completed by a trained and qualified clinician, based on clinical examination, observation and questioning of the subject. The UPDRS is made up of six parts. In this study, only Part III of the UPDRS will be used, which is a motor evaluation. The UPDRS-III is the primary endpoint in this study.

UPDRS-III is a motor evaluation, consisting of 27 items each scored on a scale of 0 to 4, with higher scores indicating greater severity of the motor symptom. UPDRS-III total is the sum of the 27 items, with scores ranging from 0 to 108.

A 5-item subscale of the UPDRS-III (UPDRS-5) will also be calculated. The UPDRS-5 combines scores from 5 items:

- rest tremor
- action tremor
- rigidity
- facial expression
- bradykinesia.

Thus, UPDRS-5 is the sum of these items, with scores ranging from 0 to 56, with higher scores indicating greater severity of the motor symptoms.

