### 10.2. Sample Size Considerations

The sample size is based on assumptions of treatment benefit for one primary endpoint, the UPDRS- III total score. A sample size of 70 subjects per treatment group will allow a treatment difference of 4 points between placebo and active treatment in the change from baseline in UPDRS- III score to be detected with 88% power and a 0.05 significance level assuming an underlying standard deviation (SD) of 7.5

There are two secondary endpoints:

- ADAS-Cog 11 total score. A sample size of 80 subjects per treatment group will allow a treatment difference of 3 points between placebo and active treatment in the change from baseline in ADAS-Cog-11 score to be detected with 88% power and a 0.05 significance level assuming an underlying standard deviation (SD) of 6. Under the assumptions of a 2.5, 2.0 and 1.5-point treatment effect, the power is 74%, 55% and 35%, respectively.
- CIBIC+. A sample size of 80 subjects per treatment group will allow a treatment difference of 0.5 points between placebo and active treatment in the observed values in the CIBIC+ to be detected with 91% power and a 0.05 significance level assuming an underlying standard deviation (SD) of 0.95. Under the assumptions of a 0.4 and 0.3-point treatment effect, the power is 75% and 51%, respectively. Randomization will be stratified according to Baseline MMSE score in the groupings of 14-17 points, 18-21 points and 22-26 points and according to whether subjects are or are not taking a cholinesterase inhibitor as a concomitant medication.

Randomization will be stratified according to Baseline MMSE score in the groupings of 14-17 points, 18-21 points and 22-26 points and according to whether subjects are or are not taking a cholinesterase inhibitor as a concomitant medication.

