### **10.4.1. Primary Efficacy Analyses**

The primary efficacy endpoint is the change from Baseline in the UPDRS-III total score at Week 24. The primary method of analysis will be using a mixed model for repeated measures (MMRM), with supportive method being the Wilcoxon rank statistic (a nonparametric test).

For the primary efficacy and secondary efficacy variable ONLY, in addition to the primary pairwise analyses, a table will be presented that will compare the POOLED data (pooled across the 35 mg and 70 mg Intepirdine arms) vs placebo. This will be done ONLY for the MMRM analysis.

Primary treatment comparisons between Intepirdine and placebo will be performed on the change from Baseline to Week 24 using an MMRM with restricted maximum likelihood estimation, an unstructured covariance matrix, and the Kenward-Roger approximation for denominator degrees of freedom. The model will include terms for treatment, visit, treatment by visit interaction, pooled geographic region, baseline MMSE score, the baseline value, and the baseline value by visit interaction.

As additional supportive information, treatment differences at each post baseline visit will also be derived using the MMRM model; however, primary inferences will be drawn from treatment differences derived from the MMRM models at Week 24.

The estimated treatment difference (“Intepirdine 35mg – Placebo” and “Intepirdine 70mg – Placebo”) at each visit will be displayed in the summary of statistical analysis together with the 95% confidence interval and the associated p-value.

No imputation of the missing values will be performed for the primary analyses, ie, the data used in the analysis will be the actual observed responses at each visit.

Least Squares Means for each visit will also be presented with the standard error and the number of subjects contributing to the Least Squares Means. Least Squares Means and estimated treatment differences for each visit and the associated 95% confidence interval will be displayed graphically.

The nature of missing data will be explored and the extent of missing data pattern will be summarized. Details will be provided in the SAP.

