## 7.8. Subgroups

While this study is not powered for subgroup analyses, the primary and secondary efficacy endpoints will be analyzed by defined subgroups. Additional subgroups may be added as the data dictate, and subgroup analysis may be performed on other variables. If the total number of subjects in a subgroup is < 10% of the total number of randomized subjects, the analysis for that subgroup may not be performed.

Assessment of safety by subgroups will be performed for OTAEs.

- UPDRS based on baseline score
  - UPDRS  $\leq 10$  and  $>10$
  - UPDRS  $<$  Baseline Overall Median and  $\geq$  Baseline Overall Median (using overall SAFETY Population)
- Cognitive Severity based on baseline MMSE
  - 14-19 and 20-26
- Geographic Region
  - US
  - EU and Canada (English speaking)
  - All other Europe (non-English speaking)
- Age (years)
  - $<$  Median and  $\geq$  Median (using overall SAFETY Population)
  - $<65$  and  $\geq 65$
- Gender
  - Female and Male
- Race
  - White and Non-White. Not that a few patients may be excluded from this analysis as their country privacy laws prohibit collection of race.
- Ethnicity

- Hispanic and Not Hispanic
- Use of Acetylcholinesterase medications
  - Using AChEIs vs Not Using AChEIs
  - Using Donepezil
  - Using Rivastigmine
- Use of Anti-parkinsonian medications (including but not limited to L-dopa, dopamine agonists, and monoamine oxidase inhibitors)
  - Using
  - Not using

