#### 9.3.1. MMRM

Primary treatment comparisons between Intepirdine and placebo will be performed on the change from Baseline to Week 24 using an MMRM with restricted maximum likelihood estimation, an unstructured covariance matrix, and the Kenward-Roger approximation for denominator degrees of freedom. The model will include terms for treatment, visit, treatment by

visit interaction, pooled geographic region, baseline MMSE score, the baseline value, and the baseline value by visit interaction.

- The region by treatment interaction term will be evaluated at the 10% level of significance; if the interaction term is found to be significant, it will be included in the MMRM model. Note, this applies to ALL MMRM models.
  - For the by-region Subgroup analyses, where, because the subgroup analyses by Region only include 1 region, the interaction makes no sense. The same MMRM model is also used for subgroups for the primary efficacy endpoint, as appropriate.

As additional supportive information, treatment differences at *each post baseline visit* will also be derived using the MMRM model; however, primary inferences will be drawn from treatment differences derived from the MMRM models at Week 24.

The estimated treatment difference (“Intepirdine 35mg – Placebo” and “Intepirdine 70mg – Placebo”) at each visit will be displayed in the summary of statistical analysis together with the 95% confidence interval and the associated p-value.

No imputation of the missing values will be performed for the primary analyses, ie, the data used in the analysis will be the actual observed responses at each visit.

Least Squares Means for each visit will also be presented with the standard error and the number of subjects contributing to the Least Squares Means. Least Squares Means and estimated treatment differences for each visit and the associated 95% confidence interval will be displayed graphically.

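### The primary UPDRS-III rating has only an indirect time-of-day anchor and no link to the last anti-parkinsonian dose, and the primary MMRM omits baseline anti-parkinsonian use; some precision is lost, but validity is not affected.

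*Protocol*

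**What the plan says.** Protocol 10.4.1 states the endpoint: "The primary efficacy endpoint is the change from Baseline in the UPDRS-III total score at Week 24". For the rating itself, Protocol 8.3.1.2 says only that "It is completed by a trained and qualified clinician, based on clinical examination, observation and questioning of the subject". No section sets a UPDRS-III clock time or an interval since the last anti-parkinsonian dose.

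For the CDR System, Protocol 8.1 says "Every effort should be made to administer the CDR computerized assessment system within" 1 hour of the Baseline time of day, citing circadian fluctuation in scores. Section 8.1 also asks for the CDR first, followed by the other efficacy scales in a constant order, when possible. It allows assessments to be split across days inside the visit window.

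Concomitant medications are recorded, but under Protocol 7.9.1 "the minimum requirement is to record the drug name and dates of administration". The time of the last dose need not be captured.

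Beyond treatment, visit and their interaction, the primary model in SAP 9.3.1 lists "visit interaction, pooled geographic region, baseline MMSE score, the baseline value, and the baseline value by visit interaction". The sample code in SAP 9.3.1.1 has no anti-parkinsonian term either. Randomisation is stratified by MMSE group and cholinesterase inhibitor use (Protocol 7.2). SAP 7.8 does define a using / not using subgroup: "Use of Anti-parkinsonian medications (including but not limited to L-dopa, dopamine agonists, and monoamine oxidase inhibitors)".

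**The concern.** The plan treats anti-parkinsonian drugs as able to move the UPDRS-III. The UPDRS Primary Analysis Population (Protocol 10.3.1, SAP 7.4) excludes certain subjects whose score improves or stabilises after an increase in such a drug. That rule deals with on-study increases. It does not deal with baseline use or with when in the day a subject is rated.

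Each subject's primary change score rests mainly on one Baseline and one Week 24 rating. If those ratings fall at different times of day, or at different intervals after a dose, any motor difference between the two states enters the change score as variation unrelated to study treatment. A baseline factor that predicts change but is left out of the model also stays in the residual variance. Either would widen the confidence interval for the primary comparison.

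**Working it through.** **Inputs.** Protocol 10.2: "A sample size of 70 subjects per treatment group will allow a treatment difference of 4 points between placebo and active treatment" in UPDRS-III change, "to be detected with 88% power and a 0.05 significance level assuming an underlying standard deviation (SD) of 7.5". Tests are two-sided (Protocol 10.1). The documents give no size for timing variation, no share of subjects on anti-parkinsonian drugs, and no user versus non-user difference. Those values are assumptions below.

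**Stated power.** Noncentrality = 4 / (7.5 × √(2/70)) = 3.155, with 138 degrees of freedom and a critical t of 1.977. Power is 88.0% (88.4% by normal approximation). The plan's 88% reproduces.

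**Timing variation already inside the SD of 7.5.** Let a share p of subjects carry timing SD s at each rating, with correlation r between the Baseline and Week 24 errors. The variance added to the change score is 2·s²·p·(1 − r). Removing all of it leaves SD = √(56.25 − 2·s²·p·(1 − r)), since 7.5² = 56.25. Power is by noncentral t with 70 per arm.

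| Assumption | s | Variance removed | SD left | Power |
|---|---|---|---|---|
| p = 25%, r = 0.5 | 2 | 1.00 | 7.43 | 88.5% |
| | 3 | 2.25 | 7.35 | 89.2% |
| | 4 | 4.00 | 7.23 | 90.2% |
| p = 50%, r = 0 | 2 | 4.00 | 7.23 | 90.2% |
| | 3 | 9.00 | 6.87 | 92.8% |
| | 4 | 16.00 | 6.34 | 95.9% |

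Both blocks assume complete removal, which no scheduling rule achieves, so each figure is a ceiling for its row.

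**Covariate alone.** If half the subjects use these drugs, and users differ from non-users by d points in change after adjustment for the existing terms, the variance explained is 0.5 × 0.5 × d² = 0.25·d².

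| d | SD left | Power |
|---|---|---|
| 1 | 7.48 | 88.1% |
| 2 | 7.43 | 88.5% |
| 3 | 7.35 | 89.2% |
| 4 | 7.23 | 90.2% |

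**Contrast case: timing variation on top of 7.5.** With p = 50% and r = 0, SD = √(56.25 + s²) = 7.76, 8.08 and 8.50 for s = 2, 3 and 4. Power is then 85.7%, 82.9% and 78.9%.

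**The case against.** The strongest reply is that clock time is already handled where it matters. The schedule (Protocol Table 2) has the CDR at both Visit 3 and Visit 12. It should come first, near its Baseline time, with the other scales following in constant order. A fixed sequence from an anchored start also anchors the UPDRS-III, and for a subject with regular dosing times it roughly anchors the dose interval. Visit 4 has a UPDRS-III without a CDR, but Week 1 is not the primary time point. This largely stands. What remains is that the anchor is indirect, is qualified by when possible, and disappears when assessments are split across days.

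The contrast with the CDR should not be overdrawn. A reader might infer that CDR timing is fixed while the UPDRS-III is uncontrolled. In fact the CDR rule is itself a best-effort target, no firmer than the order rule.

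The documents describe no within-day or dose-cycle change in UPDRS-III. Their circadian reasoning concerns CDR scores and cognition. Parkinsonism is one of three core features and not mandatory for entry (Protocol 6.2), and SAP 7.8 plans a subgroup with baseline UPDRS of 10 or less, so the affected share may be small. These points stand, and they are why the size can only be assumed.

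On the covariate, baseline UPDRS-III and its interaction with visit are already in the model, so the extra gain is probably small. The 90% figure needs users and non-users to differ by 4 points after adjustment, as much as the whole assumed treatment effect. That also stands. It limits the benefit but gives no reason to omit a factor the trial already collects.

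**Conclusion.** The point holds as a modest loss of precision on the primary endpoint. Under the assumptions shown, better timing control would be worth from about half a percentage point of power to about 8 points. The upper end requires half of subjects affected, independent errors and complete removal. The covariate would be worth about 0 to 2 points.

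Three stronger readings are tempting and not supported:

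- **The result is biased or type I error is inflated.** Under blinded randomisation, timing variation is expected to fall equally on the arms.
- **The 88% power is wrong.** It reproduces from the plan's own inputs.
- **True power is nearer 79% to 86%.** This requires 7.5 to be an SD that excludes timing variation. The sample-size section does not say so. If 7.5 already includes it, there is only a possible gain.

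**What to change.** 1. **Before unblinding, at no data cost.** In SAP 9.3.1 and 9.3.1.1, add baseline anti-parkinsonian use (yes/no), with the drug classes already named in SAP 7.8, as a covariate in the UPDRS-III and UPDRS-5 models. SAP section 2 says analysis decisions are made before unblinding, so the change belongs there.

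2. **Cheap.** In Protocol 8.1, extend the CDR wording to the UPDRS-III: every effort to rate within 1 hour of the Baseline clock time at each visit where it is scheduled, including Visit 13, and on the same day as the CDR where both are scheduled. Record the rating time and the time of the last anti-parkinsonian dose in the eCRF, and specify a sensitivity analysis that uses them. Do not require a matched dose interval: it could conflict with the clock-time target when a subject's dosing times shift. Nothing here changes any subject's medication.

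The cost is scheduling care, two eCRF fields, one model term and one sensitivity analysis. SAP section 3 records that the safety committee has already met on visit frequency, so the trial was under way. Times may therefore be missing for subjects already past Baseline, and the sensitivity analysis should state how many subjects have them.

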### **8.3.1.3. Alzheimer's Disease Assessment Scale – Cognitive Subscale (ADAS-Cog)**

The 11-item and 13-item ADAS-Cog ([Rosen et al., 1984](#)) assesses a range of cognitive abilities including memory, comprehension, orientation in time and place, and spontaneous speech. Most items are evaluated by tests, but some are dependent on clinician ratings on a 5-point scale. The ADAS-Cog 11 is the secondary endpoint in this study. The ADAS-Cog 11 total score range is from 0 to 70, with a higher score indicating more severe cognitive impairment. The ADAS-Cog 13 is the ADAS-Cog 11 with two additional items. Scores for the ADAS-Cog 13 item range from 0 to 85 with higher scores indicating greater dysfunction. The scale takes approximately 30 to 40 minutes to administer. This scale will be administered by a rater who is trained and certified for this study.

### **8.3.1.4. Clinician's Interview-Based Impression of Severity (CIBIS) and Clinician's Interview-Based Impression of Change Plus Caregiver Interview (CIBIC+)**

The CIBIC+ assessment ([Schneider et al., 1997](#)) measures the global functioning of the subject through structured interviews with both the subject and caregiver. The Clinician's Interview-Based Impression of Severity (CIBIS) will be administered at Baseline and the CIBIC+ will be administered at subsequent study visits. The change from Baseline is recorded on a 7-point scale with a score of 4 indicating no change, scores above 4 indicating worsening, and scores below 4 indicating improvement. This scale will be administered by a rater who is trained and certified

for this study, and who is independent of other cognitive and functional rating scales. Every effort should be made to have the same CIBIS/CIBIC+ rater for each subject for the duration of the study.

### 8.3.1.5. Cognitive Drug Research (CDR) Computerized Assessment System

The CDR computerized assessment system is a computerized battery of cognitive tests (Simpson et al., 1991; Keith et al., 1998). The CDR computerized assessment system includes tests of attention and information processing speed (Simple Reaction Time, Choice Reaction Time, and Digit Vigilance), verbal and visuospatial working memory (Numeric and Spatial Working Memory) and verbal and visual episodic memory (Immediate and Delayed Word Recall, Word Recognition and Picture Recognition).

The CDR computerized assessment system will be administered at the study sites by trained administrators. During the Screening visit (Visit 1) and Visit 2, the CDR computerized assessment will be administered as training sessions to overcome test anxiety, ensure the patient is able and willing to undergo testing, and overcome initial training effects in order that a stable score is subsequently obtained at Baseline (Visit 3). All tasks are computer-controlled. The information is presented on the screen of a notebook computer and the responses recorded via a response module containing two buttons, one marked 'NO' and the other 'YES'. The test administrator sits with the patient throughout testing, explains each test using pre-set instructions, initiates each test and ensures the patient performs it appropriately. Patients should not smoke or drink caffeine containing drinks for a minimum of 1 hour prior to testing on the study days.

When possible, the CDR computerized assessment system should always be the first assessment conducted, and should be administered, within  $\pm 1$  hour of the time of Baseline administration at all subsequent visits to control for potential impact of circadian variation in performance.

The tests are administered in the following order:

- Immediate Word Recall: A list of 12 words is presented on the screen at the rate of 1 every 2 seconds for the patient to remember. The patient is then given 1 minute to recall as many of the words as possible.
- Picture Presentation: A series of 14 pictures is presented on the screen at the rate of 1 every 3 seconds for the patient to remember.
- Simple Reaction Time: The patient is instructed to press the 'YES' response button as quickly as possible every time the word 'YES' is presented on the screen. Thirty stimuli are presented with a varying inter-stimulus interval.
- Digit Vigilance: A target digit is randomly selected and constantly displayed to the right of the screen. A series of digits is then presented in the center of the screen at the rate of 80 per minute and the patient is required to press the 'YES' button as

quickly as possible every time the digit in the series matches the target digit. There are 15 targets in the series. The task lasts for 3 minutes.

- **Choice Reaction Time:** Either the word 'NO' or the word 'YES' is presented on the screen and the patient is instructed to press the corresponding button as quickly as possible. There are 30 trials for which each stimulus word is chosen randomly with equal probability and there is a varying inter-stimulus interval.
- **Spatial Working Memory:** A picture of a house is presented on the screen with 4 of its 9 windows lit. The patient has to memorize the position of the lit windows. For each of the 36 subsequent presentations of the house, the patient is required to decide whether or not the 1 window that was lit was also lit in the original presentation. The patient responds by pressing the 'YES' or 'NO' buttons as appropriate, as quickly as possible.
- **Numeric Working Memory:** A series of 3 digits is presented for the patient to hold in memory. This is followed by a series of 18 probe digits for each of which the patient has to decide whether or not it is in the original series and press the 'YES' or 'NO' response button as appropriate, as quickly as possible.
- **Delayed Word Recall:** The patient is again given 1 minute to recall as many of the words as possible.
- **Word Recognition:** The original words plus 12 distracter words are presented one at a time in a randomized order. For each word the patient is required to indicate whether or not the patient recognizes it as being from the original list of words by pressing the 'YES' or 'NO' button as appropriate, as quickly as possible.
- **Picture Recognition:** The original pictures plus 14 distracter pictures are presented one at a time in a randomized order. For each picture the patient has to indicate whether or not the patient recognizes it as being from the original series by pressing the 'YES' or 'NO' button as appropriate, as quickly as possible.

Seven domains will be calculated from the CDR computerized assessment system tests (Power of Attention, Continuity of Attention, Cognitive Reaction Time, Response Variability, Quality of Working Memory, Quality of Episodic Secondary Memory, and Speed of Memory). Table 3 and Table 4 provide details on how these 7 domains are calculated.

